4.2.6. Subpopulations

Subgroup analyses will be performed for each co-primary endpoint and for BMD.

Subgroups include:

- Race: Black or African American, Other
- Ethnicity: Hispanic or Latino, Not Hispanic or Latino
- Age group 1 (<median value at baseline, ≥ median value at baseline) (based on FAS population)
- Age group 2 (<25, ≥ 25 to < 35, ≥ 35 to < 45, ≥ 45)
- Weight: < median value at baseline, ≥ median value at baseline (based on FAS population)
- BMI group 1 (< median value at baseline, ≥ median value at baseline) (based on FAS population)
- BMI group 2 (< 20, ≥ 20 to < 25, ≥ 25 to < 30, and ≥ 30)

CRS-BS-TP-000005 V 1.0

Page 38 of 127

Cytel Confidential: This is a controlled document and shall not be changed, saved, copied or reproduced by any unauthorized

Sponsor:	ObsEva		
Protocol:	18-OBE2109-003		
Document Version No.:	V5.0 Document Date: 13-JUN-2022		13-JUN-2022

- Baseline analgesic use: Subjects who took no rescue medication for endometriosis pain at baseline, subjects who took any NSAIDS and Narcotics at baseline
- Baseline pain VRS scores for dysmenorrhea (DYS), non-menstrual pelvic pain (NMPP), and dyspareunia: < median value at baseline, ≥ median value at baseline (based on FAS population)
- Time since endometriosis diagnosis (time in years): < 2 years, $\ge 2 < 5$ years, and ≥ 5 years
- History of pregnancy at baseline Yes, No

A subgroup analysis will be performed for the secondary endpoint of dyspareunia on subjects who have a mean dyspareunia score >1 at baseline. Detailed analysis is described in Section 4.6.

4.2.7. Withdrawals, Dropouts, Loss to Follow-up

In general, there will be no substitutions made to accommodate missing data points due to withdrawals, dropouts and loss to follow-up. All data recorded on the CRF will be included in data listings that will accompany the clinical study report.

In case of early discontinuation, the subject will be instructed to complete the relevant eDiary questionnaires as soon as possible upon treatment discontinuation.

Subjects who did not receive the study drug will be withdrawn from the study and no further study procedures will be performed.

Withdrawal during treatment period:

Subjects who discontinue between Day 1 and Month 3 should undergo the procedures required at Month 6 (except the DXA scan and the endometrium biopsy if a biopsy was obtained at screening) and will not enter the 6-month follow-up period.

Subjects discontinuing the study treatment between Month 3 and Month 6 should undergo the procedures required at Month 6. These subjects will enter a 6-month follow-up period and will continue daily eDiary recording for 6 months and up to Month 6 FU visit in order to continue to collect efficacy data.

PK sampling is not required if the subject had no IMP administration the day prior to the withdrawal visit.

Withdrawal during follow-up period:

Subjects discontinuing participation in the study during the follow-up period should undergo the procedures required at Month 6 FU visit, which includes completion of all ClinRO and ePRO questionnaires, except the DXA in case of discontinuation before Month 3 FU visit.

Subject Replacement:

Discontinued subjects who did not receive the study drug may be replaced.

Sponsor:	ObsEva		
Protocol:	18-OBE2109-003		
Document Version No.:	V5.0		

Additional subjects may be recruited due to subjects who were discontinued due to ALT, AST, GGT or total bilirubin ≥ 2 times the upper limit of normal at Day 1, or due to a clinically significant biopsy finding at Day 1 (treatment start), or due to high calcium level at Day 1.

4.2.8. Missing, Unused, and Spurious Data

4.2.8.1. Efficacy Endpoints Missing Data

Summary statistics will be based primarily on non-missing values. The planned statistical analyses aim to estimate the efficacy of linzagolix versus placebo while under randomized treatment and therefore lack of data after treatment discontinuation will not be considered as missing for these analyses.

Subjects who cannot be assessed as responders for the co-primary efficacy endpoints, e.g. due to lack of on treatment pain data (i.e. subjects who received less than 28 days of treatment), will be considered as non-responders. In addition, for endpoints assessing the numeric change from baseline, such subjects will be assigned a change from baseline of zero. It is expected that very few subjects will be affected by these rules.

There may be missing data during the screening period and whilst under treatment, for example, missed days of completing the eDiary. The primary analyses will use observed data only in such cases provided that a minimum number of completed daily eDiary entries are available. This effectively assumes that the individual values such as daily eDiary assessments (observed or not) are independent of being missing.

Further details on the handling of missing values and the methods and planned sensitivity analyses to check the robustness of the analysis results under alternative assumptions with regards to missing data are provided in the analyses sections. As additional analyses, in order to estimate the effect of treatment policy, a reference based multiple imputation approach will be used for the co-primary endpoints for subjects who discontinue the study early under the assumption that the efficacy of the linzagolix treated subjects gradually transitions to that observed in the placebo subjects.

Missingness Assumptions:

Missing At Random (MAR): Missingness is independent of unobserved outcomes given observed data. Subjects with missing data can be modeled based on similar subjects with available data if we account in the model for relevant observed factors.

Missing Not At Random (MNAR): The probability of missingness depends on the unobserved outcome and cannot be predicted only based on observed data.

Multiple Imputation Methodology:

Multiple imputation inference involves three distinct steps:

Sponsor:	ObsEva		
Protocol:	18-OBE2109-00	18-OBE2109-003	
Document Version No.:	V5.0		

- 1. The missing data are filled in m times to generate m complete data sets, using defined assumptions on missingness.
- 2. The m complete data sets are analyzed using standard statistical analyses.
- 3. The results from the m complete data sets are combined to produce inferential results.

Reference-based multiple imputation:

Imputation model for the missing observations in the active treatment groups that is constructed not from the observed data in the active treatment groups but rather from the observed data in the control group. Missing observations from the control group are also imputed using observed data from the control group.

The fully conditional specification method will allow multivariate imputation of the different endpoints.

Application of multiple imputation for binary endpoints:

The two co-primary endpoints are binary endpoints derived from underlying continuous endpoints. The first step of multiple imputation will be performed on the continuous variables and transformation into a binary endpoint will be applied after imputation.

As the second step, the statistical analysis for treatment effect on binary endpoints (logistic regression) will be performed on each m imputed datasets.

Odds ratios of the contrast of interest will be presented. To obtain the combined estimates of odds ratios from each of the m models, the log of odds ratios estimates should be used in the MIANALYZE procedure, and the combined estimates should be back transformed afterwards. This is in order to fulfill the assumption that the statistics estimated from each imputed dataset are normally distributed (Ratitch, Lipkovich, & O'Kelly, 2013)

4.2.8.2. Adverse events and Concomitant Medication Missing Dates

Imputation of missing/partial AE and CM dates will be done only to identify treatment-emergent AEs.

AE onset dates:

- Partially missing AE onset dates will be imputed as follows:
 - When only Day is missing:
 - If Month & Year of the onset date are the same as Month & Year of the first administration date, the imputed onset date will be imputed as the minimum of the first administration date and the AE resolution date (imputed if needed).

Sponsor:	ObsEva		
Protocol:	18-OBE2109-003		
Document Version No.:	V5.0		

- Else if the subject entered the Extension Study and Month & Year is the same as Month & Year of the first administration date in Extension, the imputed onset date will be imputed as the minimum of the first administration date in Extension and the AE resolution date (imputed if needed).
- Otherwise, the missing day will be replaced by "1"
- When Day & Month are missing:
 - If the subject entered the Extension Study and if Year of the onset date is the same as Year of the first administration date in Extension, the imputed onset date will be imputed as the minimum of the first administration date in Extension and the AE end date (imputed if needed).
 - Else if Year of the onset date is the same as Year of the first administration date, the imputed onset date will be imputed as the minimum of the first administration date and the AE end date (imputed if needed).
 - Otherwise, the missing Day & Month will be replaced by "01 JAN."
- Completely missing onset dates for AEs
 - If the subject entered the Extension, the AE onset date will be imputed by the first administration date in Extension and the AE will be considered as treatment-emergent, unless the end date of the AE (imputed if needed) or the end year of the AE (if day and month are missing) is entered and is before the first administration date in Extension.
 - If the subject did not enter the Extension, or if the end of the AE is before the first administration date in Extension, the AE onset date will be imputed by the first administration date and the AE will be considered as treatment-emergent, unless the end date of the AE (imputed if needed) or the end year of the AE (if day and month are missing) is entered and is before the first administration date. If the end date is before the first administration date, the AE will not be considered as treatment-emergent.

AE end dates

- If Day only is missing, incomplete end dates will be replaced by the last day of the month, if not resulting in a date later than the date of the subject's death or date of study discontinuation. In the latter case, the date of death/date of study discontinuation will be used to impute the incomplete end date.
- If Day & Month are missing, Day & Month will be replaced by 31DEC, if not resulting in a date later than the date of the subject's death or date of study discontinuation. In the latter case, the date of death/ date of study discontinuation will be used to impute the incomplete end date.
- In all other cases the incomplete end date will not be imputed.

Sponsor:	ObsEva		
Protocol:	18-OBE2109-003		
Document Version No.:	V5.0	Document Date:	13-JUN-2022

Concomitant Medications dates

Partially missing dates for prior and concomitant medications and procedures will be imputed. Of note, imputation of missing/partial dates will be done only to identify the treatment period assignment.

- End date: Missing day will be imputed as the last day of the month, and missing month will be imputed by December, if not resulting in a date later than the date of the subject's death or date of study discontinuation. In the latter case, the date of death/date of study discontinuation will be used to impute the incomplete end date.
- Start date: Missing day will be imputed as the first day of the month, and missing month will be imputed by January.
- If the start date is completely missing, then:
 - If the end date is prior to the date of first administration of the study drug, then the medication is considered as prior
 - If the end date is prior to the date of last administration of the study drug, then the medication is considered as prior and concomitant
 - If the end date is completely missing or after the date of last administration of the study drug, then the medication is considered as prior, concomitant and post.

4.2.8.3. eDiary Devices Data Cleaning

To handle eDiary system issues, mapping rules are defined for data analysis, as described in Appendix E in Section 7.5.

In addition, the following rules are defined.

Handling of duplicate records

- A change of eDiary device vendor (vendor to Signant Health vendor) occurred during the study.
- Some subjects may have entered data in the two different devices during the transition period. In case of duplicates results on the same day for daily diaries or on the same visit for monthly questionnaires, data from the new vendor (Signant Health) will be used for analysis.
- In case of duplicates within the same device (same date, same name), the first non-empty record (with earliest date/time) should be used for analysis.

Daily Records entered after 00:00

For daily diaries, records entered with a time between 00:00 (midnight) and 02:00 AM should be considered for the previous day.

Sponsor:	ObsEva		
Protocol:	18-OBE2109-003		
Document Version No.:	V5.0 Document Date: 13-JUN-2022		13-JUN-2022

Additional rules to specific eDiary domains:

Analgesic use data:

- Analgesic use data from "Today" will be used primarily. If data from "Today" is missing, data from "Yesterday" of the following day will be considered

IMP Intake Data:

- IMP Intake data from "Today" will be used primarily. If data from "Today" is missing, data from "Yesterday" of the following day will be considered

device specific rules

NOTE: by design, when a subject is completing a questionnaire (daily or monthly) on a device, the device automatically saves all answers provided by the subject as soon as recorded, unless the subject uses the "previous" button to come back to already answered question(s) within the questionnaire and changes her answer(s) prior to finishing the questionnaire.

There are several triggering questions in the study questionnaires: the next question(s) presented to the subject will depend on the answer chosen by the subject to the current question.

Due to device design issue, when an answer to a triggering question has been changed by the subject (using previous button), the device keeps subsequent answer(s) to the previously triggered question(s), even if this/these question(s) is/are no longer relevant considering the new answer to the triggering question.

The agreed rules consider the last entry made by the subject i.e. the entry that would have not allowed her to provide additional data if it had been her initial answer (in Signant Health device, the intermediate answers are not saved and will not be present in the database; the agreed rules are aligned with this functioning).

Analgesic use data:

- If answer to question "Did you take any provided/prescribed analgesic for your endometriosis related pain?" is "Yes" or empty but the number of ibuprofen intakes and narcotic analgesics intakes are both 0, it will be considered that no analgesic was used on that day.
- If answer to question "Did you take any provided/prescribed analgesic for your endometriosis related pain?" is "Yes" or empty, but question to Ibuprofen intake is "No" and the number of ibuprofen intakes is not zero, it will be considered that no ibuprofen was used on that day. The same rule will be applied for narcotic analgesics.

Sponsor:	ObsEva		
Protocol:	18-OBE2109-003		
Document Version No.:	V5.0 Document Date: 13-JUN-2022		13-JUN-2022

- If answer to question "Did you take any provided/prescribed analgesic for your endometriosis related pain?" is "No" and the number of ibuprofen intakes and narcotic analgesics intakes are not 0, it will be considered that no analgesic was used on that day and following answers will be ignored.
- If answer to "Did you take any provided/prescribed analgesic for your endometriosis related pain?" is "No" and answer to question Ibuprofen intake is "Yes", but the number of Ibuprofen intakes is 0, it will be considered that no ibuprofen was used on that day. The same rule will be applied for narcotic analgesics.

Dyspareunia VRS Data:

- when question "Did you have any sexual intercourse?" is answered "No, I was not sexually active for reasons other than my endometriosis" or "No, I avoided sexual intercourse because of anticipation of pain" and there is an answer to question "How did your endometriosis related pain interfere with sexual intercourse?", only the "No" answer will be considered.
- when question "Did you have any sexual intercourse?" is blank and there is an answer to question "How did your endometriosis related pain interfere with sexual intercourse?", consider that "Yes" was answered to "Did you have any sexual intercourse".

HRUQ Data:

- when answer to triggering question 1 is "No" and at least one answer to question 2 to 6 (any answer different from 0) is present, ignore answer 2-6 in the analysis
- when answer to triggering question 7 is "No" and at least one answer to questions 8 to 9 (any answer different from 0) is present, ignore answers 8-9 in the analysis
- For questions 8-9, consider the number of times whatever the answer provided for "procedures" (i.e., if it is NO include number of times if different than 0)

HRPQ Data:

- when answer to question 9 is different than "endometriosis symptoms or its treatment(s) forced me to work part-time when I wanted to work full-time" and question 9bis is different than 0, ignore answer 9bis in the analysis.
- when answer to question 9 is different than "endometriosis symptoms or its treatment(s) kept me from having a job when I wanted to work full-time" and question 9ter is different than 0, ignore answer 9ter in the analysis.
- when answer to question 9 is different than "endometriosis symptoms or its treatment(s) kept me from having a job when I wanted to work part-time" and question 9quater is different than 0, ignore answer 9quater in the analysis

Sponsor:	ObsEva		
Protocol:	18-OBE2109-003		
Document Version No.:	V5.0		

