2. STUDY DESIGN

2.1. Synopsis of Study Design

This is a prospective, randomized, double-blind, placebo-controlled study to demonstrate the efficacy and safety of linzagolix administered orally once daily at doses of 75 mg alone and 200 mg in combination with low dose ABT (E2 1 mg/NETA 0.5 mg) versus placebo in the management of moderate to severe EAP in women with surgically confirmed endometriosis.

The study starts with an approximately 3-month screening period during which subjects will receive no study drug. Eligibility will be confirmed based on data collected during the screening period. After randomization, a 6-month Treatment Period will follow. Subjects will be randomized to one of the three treatment groups:

1. Linzagolix 75 mg

- 2. Linzagolix 200 mg combined with ABT
- 3. Placebo

Randomization will be conducted via an interactive web response system (IWRS) in a 1:1:1 ratio. There will be no stratification.

At 6 months, BMD change will be assessed via DXA measurement. Eligible subjects who have completed the 6-month treatment period may enter a separate extension study for 6 additional months of active treatment (no placebo control). In this extension study, subjects who previously received placebo will be randomly switched to one of the two active treatments (75 mg alone or 200 mg + ABT). Subjects who received active treatment will continue with the same treatment.

Subjects who decline to participate to or do not qualify for the extension study and who were exposed to at least 3 months of treatment will enter a 6-month drug-free follow-up. At the end of the 6-month follow-up period, subjects with a BMD decrease from baseline of >1.5% for lumbar spine and >2.5% for total hip will have an additional DXA scan 6 months later. Subjects who discontinue treatment prior to Month 3 will not enter the follow-up period.

[figure not shown]
The main analysis will be performed after 6 months of treatment and will include all of the subjects' data up to Month 6. The primary endpoint analysis will be based on subjects' data up to Month 3.

The study will last on average 15 months for each patient; 3-month Screening Period, 6-month Treatment Period and 6-month Follow-up (with 1 month being defined as 28 days/4 weeks). This estimated duration excludes any washout period.

Sponsor:	ObsEva						
Protocol:	18-OBE2109-00	18-OBE2109-003					
Document Version No.:	V5.0	Document Date:	13-JUN-2022				

A schematic of the study design is shown in Figure 1.

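### For extension entrants, an adverse event with a wholly missing or year-only onset can be dated to the first extension dose, later than its own report, and so drop out of the placebo-controlled tables

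*SAP*

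**What the plan says.** SAP 4.2.8.2 has three branches for an incomplete AE onset date.

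- **Wholly missing.** "If the subject entered the Extension, the AE onset date will be imputed by the first administration date in Extension", and the event is flagged treatment-emergent. The exception is an end date or end year that "is entered and is before the first administration date in Extension"; the first main-study dose is then used.
- **Day and month missing.** The first test is whether "the subject entered the Extension Study and if Year of the onset date is the same as Year of the first administration date in Extension". If so, onset is the earlier of the first extension dose and the AE end date. The main-study year is tested only after that.
- **Day missing.** The order is reversed. The first test is "If Month & Year of the onset date are the same as Month & Year of the first administration date", meaning the main-study first dose. The month of the first extension dose comes second. Otherwise the first of the recorded month is used.

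Four other places determine what the imputed date does.

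- SAP 5 states that extension treatment starts on the Month 6 day.
- SAP 4.2.11 ends the main treatment period the day before Month 6 and, for entrants, assigns AE data on the Month 6 day to the extension.
- SAP 4.8.2 ends the treatment-period AE table on that same earlier day. Its 30-day carry-back covers only women who enter neither the follow-up nor the extension.
- SAP 2.1 says that in the extension "subjects who previously received placebo will be randomly switched to one of the two active treatments".

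**The concern.** The branches use the onset fragment, the two first-dose dates and the end date. They do not use the date or visit at which the event was recorded. AEs are recorded at every visit (Protocol 10.2.2 and 12.5), so an event can be on record months before the extension starts and still be dated to the first extension dose. That onset is impossible, and it moves the event out of the main treatment-period table.

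The main study is the only placebo-controlled part of the programme described here, and its AE tables are the controlled safety evidence. The rule operates only in women who went on to the extension, a group defined after randomization. For a woman on placebo, the imputed onset coincides with her first active dose.

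The SAP is also inconsistent with itself. The day-only and year-only branches use opposite precedence without a stated reason. In the same section, a medication with both dates wholly missing counts as prior, concomitant and post-treatment, so no possible period is dropped; an AE with the same missing dates is placed in the extension alone.

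**Working it through.** The plan gives no figure to reproduce, so the check applies the rule to hypothetical events.

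**1. An impossible date (illustration).** Take Day 1 = 1 March 2021. Month 2 is Day 57 (SAP Table 3), which is 26 April. The first extension dose is on Day 169, which is 16 August. An ongoing event reported at Month 2 with no onset date is imputed to 16 August, 169 − 57 = 112 days after it was reported. The result is the same if only the year 2021 is known.

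**2. How far the rule reaches.** Inputs from the documents: main-study days 1 to 168, with the first extension dose on Day 169 (168 days after Day 1). Assumptions not in the documents: Day 1 uniform over 365 dates, onset uniform over the 168 days, and either no end date or a known end date 7, 28 or 84 days after onset. The table gives the share of true main-study events re-dated to the first extension dose.

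| Missing part of onset | No end date | 7 days | 28 days | 84 days |
|---|---|---|---|---|
| Whole date | 100% | 4.2% | 16.7% | 50.0% |
| Day and month | 76.8% | 4.1% | 16.0% | 44.2% |
| Day only | 8.8% | 3.6% | 8.7% | 8.8% |

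These can be checked by hand:

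- *Whole date, known end date:* the event moves if it ends on or after the extension dose, a share of duration/168. 7/168 = 4.2%; 28/168 = 16.7%; 84/168 = 50.0%.
- *Day and month, no end date:* the extension starts in the same calendar year for 365 − 168 = 197 Day 1 dates (197/365 = 54%), and all those events move. For the other 168 dates, the share of onsets falling in the new year runs from 0/168 to 167/168, which sums to 83.5. (197 + 83.5)/365 = 76.8%.
- *Day only, no end date:* only onsets in the extension's start month move. The average number of main-study days in that month is 14.72, and 14.72/168 = 8.8%.

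**3. How well the end date protects.** SAP 4.2.8.2 moves a partial end date to the end of the month or, for comparison with the extension dose, uses the end year alone. For a 7-day event with a wholly missing onset, under the same assumptions and with no cap from death or study discontinuation:

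- full end date: 7/168 = 4.2%;
- end day missing: (7 + 14.72)/168 = 12.9%;
- only the end year known: all events for 197 Day 1 dates, plus a summed share of 15,183/168 = 90.4 over the other 168, so (197 + 90.4)/365 = 78.7%.

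The safeguard therefore works well with a complete end date and poorly with only an end year.

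**The case against.** The strongest counter-arguments are these.

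- **The reach is limited.** A reader might infer that every partial onset date defaults to the extension. It does not: a day-only gap tests the main-study month first and uses the extension date only in the extension's start month. Events known to have ended before the extension dose stay in the main study in every branch. Both points stand.
- **4.2.8.2 alone removes nothing.** It says AE imputation serves only to identify treatment-emergent events, and an event dated on the Month 6 day still meets that definition. This is right, but the period split in 4.2.11 and 4.8.2 then takes it out of the main table, and the carry-back does not return it.
- **No known bias between arms.** A reader might infer that the rule flatters or penalises linzagolix. It applies equally to all three arms: losing placebo events makes active drug look worse, and losing active events makes it look better. The documents do not support a net direction.
- **Crediting to active drug is an inference.** The extension is a separate study whose SAP and AE tables are not in these documents. They show that a placebo woman's event is dated to her first active dose, not how the extension tabulates it.
- **Few events.** Protocol 12.2.3 calls for onset and resolution dates on each AE report, Protocol 13.6.2 has discrepant data clarified before lock, and on-study AEs are listed and not formally tested. This limits the size but does not make an onset after the report date correct.
- **The opposite default has a cost.** Sending every event that could have begun before the extension dose to the main study would also move true extension events and, for placebo women, count events on active drug as placebo events. This is a fair point, and the fix below avoids that rule.

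**Conclusion.** The concern holds in this form. For extension entrants, an AE with a wholly missing onset, or a year-only onset in the extension's start year, is dated to the first extension dose unless it is known to have ended earlier. Because the rule ignores when the event was recorded, it can produce an onset after the report and remove a main-study event from the placebo-controlled tables. That is wrong as written.

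The percentages describe what happens to an affected event under uniform dates; they are not shares of all AEs. The number of AEs with such gaps is not in the documents and is probably small, so the effect on any table cannot be stated. This is a correctable derivation error, not evidence of a biased safety comparison.

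**What to change.** 1. Add to SAP 4.2.8.2 that an imputed onset may not be later than the date or visit at which the AE was first recorded. Any AE recorded before the first extension dose is then imputed within the main study: the first main-study dose, or the start of the known month or year if later, subject to the existing end-date rule.
2. Use the same branch order for day-only and year-only gaps.
3. For AEs first recorded after the extension dose whose onset remains ambiguous, report the count and give a sensitivity table assigning them to the main study. If the count is zero, one sentence is enough.

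The cost is a change of SAP wording, a small derivation change and one extra table. The sensitivity table may include some true extension events, which is why it should not replace the main one.
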